Comparative analyses to the Phase IV historical control arm will involve comparison of the binary shedding positivity endpoint using summary statistics, as well as 95% score-based confidence intervals for the difference in proportions at each time point.

The CCID₅₀ will be \log_{10} transformed, described with summary statistics, and compared to historical control using two-sided randomization tests and bootstrap 95% confidence intervals for the difference in median.

Time-to-shedding cessation will be summarized using quantiles and corresponding 95% confidence intervals, and tests between candidate vaccines and the historical control will be conducted with two-sided log-rank tests using a Type I error rate of 5%.

10.1.4 *Safety Data*

For an overview of primary and secondary endpoints, see Section 3.

Safety parameters will be tabulated and analyzed descriptively. Comparisons to the historical control will be based on descriptive statistics, using rates for adverse events and laboratory deviations, and continuous summaries for safety laboratory values.

Adverse Events

Analyses described below will be performed for solicited and unsolicited AEs as well as for SAEs, severe AEs.

The original terms used in the designated sections of the eCRFs by Investigators to identify AEs will be fully described and coded according to the current Medical

Dictionary for Regulatory Activities (MedDRA). For comparison with the M1 study M1 data will be recoded if necessary. All AEs will be summarized by type, seriousness, severity, causality, by group, and overall.

Separate tables and listings will be created for those subjects who died, discontinued the study vaccine due to an AE, or experienced a severe or serious AE. Summaries, listings, and narratives may be provided, as appropriate.

Clinical Laboratory Tests

Each continuous biochemistry and hematology laboratory test will be evaluated by means of descriptive statistics (i.e., number of subjects, mean, SD, median, minimum, and maximum) on the actual values, at each assessment time point and by group. Changes from baseline will also be summarized by assessment time point and by group.

Clinical laboratory test values will be evaluated according to Common Terminology Criteria for Adverse Events (CTCAE) version 4.03 (toxicity grades) or in accordance with the normal ranges of the clinical laboratory (below, within, or above normal range) for parameters for which no toxicity grades are defined.

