6.7.1 Exploratory Viral Shedding Endpoints

Throughout, viral shedding analyses will be conducted by group and dose number. The descriptive summaries below will also be computed separately by site. Between-group inferential analyses will additionally be conducted among the site in common between UAM1 and UAM4, for OPV-vaccinated subjects, if the post-dose-1 between-site GMT comparison indicates a significant difference in immunogenicity between sites. The shedding analyses will be conducted considering all available samples, collected at Days 0-10, 14, 21, 28, and 42 following each dose (with day of vaccination defined as Day 0) and additional samples collected, as necessary, to define the end of shedding for participants. All viral shedding data will be listed, including both sample collection and assay results.

Categorical summaries of type 2 viral shedding positivity (positive via PCR) and continuous summaries of viral titers (\log_{10} CCID₅₀/g among both shedders and shedders/non-shedders combined) will be produced by group and by post-vaccination day. Each of these will be augmented with two-sided 95% confidence intervals. The Clopper-Pearson exact method will be used for shedding positivity rate, and the bootstrap method (10,000 replicates, quantile method) will be used for the median \log_{10} viral titers. Subjects who are PCR-negative for viral shedding at a given time point will be assigned the value of 0 for computations involving the \log_{10} CCID₅₀/g, and values PCR positive for type 2 poliovirus but below LLOQ ($2.75 \log_{10}$ CCID₅₀/g) or above ULOQ ($8.25 \log_{10}$ CCID₅₀/g) will be assigned the corresponding value of LLOQ or ULOQ.

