A comparison of the extent of shedding among OPV-vaccinated subjects to the corresponding control data from study UAM1 will be conducted by computing the difference in viral shedding rate per study day with corresponding two-sided 95% Miettinen and Nurminen confidence intervals for the difference, and augmented with the difference in median viral shedding for the daily shedding values (\log_{10} CCID₅₀/g) as well as the AUC and SIE alongside bootstrap-based (n=10,000 replicates each) two-sided 95% confidence intervals for the difference. A listing will include the computed time-to-shedding-cessation and the corresponding censoring indicator, the AUC, and the SIE values.

Plots of the reverse cumulative distribution of the viral shedding concentrations (by study day) and each aggregate index will be generated.

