If sufficient quantities of EES and, among them, sufficient mouse paralysis is observed, model-based analyses will be used to supplement the descriptive summaries described above. (See also the section *Alternate Method for Lack of Model Fit*, below.) It is currently known that, prior to the amplification step required to conduct the assay, only 2 post-dose-1 EES are available from the historical control subjects, UAM1. It is therefore likely that model-based analyses will fail, and/or will fail to provide additional insight beyond the descriptive summaries previously described, however, model-based analyses will still be attempted.

For each vaccine group, a generalized linear mixed model (GLMM) will be fitted to the binomial count of paralyzed mice for NEARs obtained at the $4.0 \log_{10} \text{CCID}_{50}/\text{g}$ dose level. This model is given by

$$\text{logit}^{-1}(p_i) = \beta_0 + \beta_1 I_{[\text{sex}=\text{F}]} + \delta_i \quad (1)$$

where

- β_0 is the overall mean log-odds of paralysis for male mice
- β_1 is the difference in mean log-odds of paralysis between mouse gender (females minus males)
- p_i is the paralysis rate for sample (subject) i
- $\delta_i \sim N(0, \tau^2)$ is the subject-level random effect, intended to capture overdispersion due to between-sample variability in the neurovirulence of each virus population, including variability in the precise titer of inoculum

In SAS/STAT software, this model may be fitted using the PROC GLIMMIX procedure. It is preferred to use METHOD = LAPLACE in the PROC GLIMMIX statement, due to better asymptotic performance of the estimators. The SAS default method for computing degrees of freedom should be utilized for statistical tests (DDFM = BETWITHIN). SAS code to fit the model defined above is given by:

```
proc glimmix data=dat method=laplace;
  class sample sex;
  model x/n = sex / cl solution ddfm = betwithin;
  random intercept / subject=sample;
  lsmeans sex / ilink;
run;
```

where “sample” is the sample number (e.g., subject identifier providing the sample), “x” is the mouse gender-specific number of mice paralyzed, “n” is the mouse gender-specific number of

inoculated mice available for analysis, and “sex” captures the mouse gender. The dataset “dat” should contain one row for each subject, for each mouse gender. Additional options to the SAS procedure may be necessary to obtain all necessary output.

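### The bootstrap difference in median shedding against UAM1 carries no information on low-positivity days, and it is the only contrast planned for the Shedding Index Endpoint (SIE)

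*SAP*

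**What the plan says.** SAP Section 6.7.1 sets the scoring: "Subjects who are PCR-negative for viral shedding at a given time point will be assigned the value of 0 for computations" on the log10 CCID50/g scale, and PCR-positive results outside the quantitation range "will be assigned the corresponding value of LLOQ or ULOQ", that is 2.75 or 8.25. Every positive therefore scores at least 2.75.

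For OPV-vaccinated subjects, the comparison of extent of shedding with UAM1 starts by "computing the difference in viral shedding rate per study day with corresponding two-sided 95% Miettinen and Nurminen confidence intervals for the difference". It is then "augmented with the difference in median viral shedding for the daily shedding values" and for the AUC and SIE, each with "bootstrap-based (n=10,000 replicates each) two-sided 95% confidence intervals for the difference". A two-sided log-rank test of time to cessation is also planned.

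The section asks for titre summaries both among shedders and in shedders and non-shedders combined, but does not say which set the between-study median difference uses. The zero-scoring rule points to all subjects. The protocol's endpoint (Section 3.3) is the median titre among PCR-positive samples.

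Protocol Section 10.1.3 (Viral Shedding) says the log10 CCID50 will be "compared to historical control using two-sided randomization tests and bootstrap 95% confidence intervals for the difference in" median. The SAP has no randomization test for shedding, and its Section 7, on differences from the protocol, mentions only fold-rise summaries.

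**The concern.** A median ignores everything on the far side of a point mass that holds more than half the data. With negatives at 0 and positives at 2.75 or above, an arm's median is 0 on any day when fewer than half its subjects shed. If both arms are well below half, almost every bootstrap median is 0 too, and the interval closes on 0. A zero-width 95% interval looks like very precise evidence of equality, when in fact the statistic could not have shown anything else.

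The stake is the comparison of the amount of virus shed, which is part of a stated exploratory objective. It matters most late in follow-up, when positivity is likely to be lowest, and for the SIE, which averages Days 7, 14, 21 and 28.

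**Working it through.** The documents give no power or expected value for shedding, so there is no plan figure to reproduce.

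**Inputs.** Negatives 0; positives 2.75 to 8.25 (SAP 6.7.1). Planned sizes: 100 per candidate and 100 in UAM1 after dose 1; 50 and 50 after dose 2 (Protocol Section 10.2 and Appendix 3). Assumptions: the all-subject reading; the quantile bootstrap that the SAP names for single-group medians applied to the difference as well; and all positivity rates, since the documents give none for OPV-primed adults.

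**Step 1: when does the daily interval collapse?** For even n, a resampled median is above 0 only if at least n/2 of the resample is positive. With k observed positives,

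P(median* > 0) = P(Bin(n, k/n) ≥ n/2).

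If this is at most 0.025 in both arms, both percentile limits are 0.

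- n = 100: k = 39 gives 0.0165; k = 40 gives 0.0271. Limit 39/100.
- n = 50: k = 17 gives 0.0141; k = 18 gives 0.0295. Limit 17/50 = 34%.

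**Step 2: worked daily examples.** 10,000 bootstrap replicates; titres evenly spaced from 2.75 to 8.25 unless stated.

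| Positives, candidate vs control | Median difference | Rate difference, points | Mean difference |
|---|---|---|---|
| 39 vs 10 of 100 | 0 [0, 0] | 29 [17.6, 40.1] | 1.60 [0.94, 2.26] |
| 39 vs 39 of 100, all 8.25 vs all 2.75 | 0 [0, 0] | 0 [-13.4, 13.4] | 2.145 [1.29, 2.97] |
| 17 vs 5 of 50 | 0 [0, 0] | 24 [8.1, 39.6] | 1.32 [0.42, 2.23] |
| 40 vs 10 of 100 | 0 [0, 1.38] | 30 [18.5, 41.1] | 1.65 [1.00, 2.32] |
| 45 vs 10 of 100 | 0 [0, 3.25] | 35 [23.3, 46.1] | 1.92 [1.25, 2.60] |
| 60 vs 30 of 100 | 3.64 [1.42, 4.52] | 30 [16.4, 42.5] | 1.65 [0.87, 2.43] |

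The second row shows the gap. The largest titre difference that the scoring allows (mean difference 0.39 × (8.25 − 2.75) = 2.145) is invisible to both planned daily contrasts.

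**Step 3: SIE.** Assumed positivity on Days 7/14/21/28 is 40/25/15/10% vs 20/12/7/5%, with positive titres N(3.2, 1) clipped to 2.75–8.25 and n = 100 per arm. A subject's SIE is 0 only if all four days are negative. The share with SIE above 0 is:

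- independent days: candidate 1 − 0.60 × 0.75 × 0.85 × 0.90 = 66%; control 1 − 0.80 × 0.88 × 0.93 × 0.95 = 38%;
- complete clustering in the same subjects: 40% and 20%.

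Clustering thus moves the candidate arm from above one half to below it. Share of simulated trials whose interval excludes 0:

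| Within-subject correlation | 0.3 | 0.6 | 0.9 |
|---|---|---|---|
| Difference in medians | about 35% | about 1% | 0% |
| Difference in means | about 96% | about 93% | about 85% |

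Repeat runs differ by a few percentage points.

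**Step 4: AUC.** With assumed positivity of at most 39% (candidate) and 20% (control) on every day, the median interval was never [0, 0]. It excluded 0 in 100%, 99% and 35% of trials at correlations 0.3, 0.6 and 0.9. Because it pools many days, most subjects have a non-zero AUC.

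**Step 5: which daily repair works?** Equal positivity in both arms, a 1 log10 titre shift, n = 100 per arm. At 10%, 20% and 35% positive, the all-subject mean difference detected the shift in 9%, 11% and 19% of trials; a shedders-only median difference did so in 44%, 66% and 90%. Across repeat runs the ranges were 8–23% and 37–94%.

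**The case against.** The strongest reply is that the median difference is an addition, not the main contrast. The same sentence of the SAP puts the daily positivity difference first. That contrast detects gaps in positivity well: its power at n = 100 per arm is 81% for 10% vs 25%, 99% for 10% vs 35% and 88% for 20% vs 40%. The log-rank test covers duration, and the reverse cumulative distribution plots show both the zeros and the titres. On a shedders-only reading the daily point mass disappears altogether. All of this stands, and it confines the daily problem to differences in quantity at similar, low positivity.

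A reader might infer that the result is 0 with interval [0, 0] whenever most subjects are negative, whatever the candidate does. The plan's rules do not imply that. With 40 to 49 of 100 positive the estimate is 0 but the interval has width, and a majority-positive candidate gives a non-zero difference.

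A reader might also take SAP Section 6.7.2, which reports that "only 2 post-dose-1 EES are available from the historical control subjects, UAM1", as proof of low positivity in the control. Those samples (EES) are ones above 4.0 log10 CCID50/g, and the UAM1 synopsis planned shedding tests on a subset of stools. The figure suggests little high-titre shedding but gives no PCR positivity rate.

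Finally, the protocol names no statistic for its randomization test and pairs it with a difference in medians. A median-based version would degenerate in the same way, so restoring it helps only if the statistic is changed.

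**Conclusion.** The concern holds in a limited form. On the all-subject reading, the daily median contrast is uninformative when both arms are at or below about 39% positive at n = 100, or 34% at n = 50, and no planned between-study contrast then measures daily quantity. The SIE is the more exposed measure. It has no alternative contrast, and the median rule loses most of its power when late shedding is uncommon and concentrated in the same subjects. AUC is affected much less.

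The thresholds follow from the scoring rule, the planned sizes and the percentile bootstrap. The power figures rest on assumed positivity, titres and correlation, and show direction and rough size only. Separately, a test in the protocol is missing from the SAP without being listed as a change.

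The SAP calls these analyses descriptive and the endpoints exploratory, and no primary conclusion depends on them. The change is worth making but modest.

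**What to change.** Amend the between-study comparison in SAP Section 6.7.1:

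1. For SIE, and for AUC for consistency, make the contrast with UAM1 the difference in means, with the same 10,000-replicate bootstrap 95% interval. Keep medians as descriptive summaries.
2. For daily titre, state the analysis set and compare titres among shedders, in line with the protocol endpoint, alongside the existing rate difference. If an all-subject median difference is still shown, footnote zero-width intervals as uninformative.
3. Restore the two-sided randomization test on a rank-sum or mean statistic, or list its removal in SAP Section 7.

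The cost is SAP wording and one changed statistic in an existing bootstrap program; no new data are needed. Two drawbacks should be stated in the SAP. The mean depends on the values assigned to negatives and to positives below LLOQ, and the shedders-only contrast conditions on a post-vaccination outcome, so it must be read together with the positivity rates.

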6.7.2 Exploratory Analysis of Neurovirulence of Shed Virus

Stool samples positive for type 2 viral shedding of sufficient quantity to enable an evaluation of the neurovirulence of the virus in a transgenic mouse assay may be selected from the stool samples processed through the PCR and CCID₅₀ assays. Not all such samples will be assessed for neurovirulence, and sub-sampling of groups or sub-sampling within groups may occur. The sub-sampling methodology used, if any, will be fully described in the clinical study report. It is anticipated that sampling will focus on Exploratory Endpoint Samples (EESs), defined as the last PCR-positive stool sample with a CCID₅₀ above the predetermined cutoff of 4.0 \log_{10} CCID₅₀/g of stool, and a comparative evaluation of EES from OPV-vaccinated subjects in UAM1 and in UAM4 (both candidate vaccines in M4 vs the common M1 control) will be conducted, and the

results from IPV-vaccinated subjects will be descriptive (including non-comparative model-based methods described below).

For details of the conduct of the neurovirulence assay, refer to [1]. Validity criteria for the back-titration of inoculum are established to ensure the dose of inoculum is similar across assay iterations. In the single-dose assay statistical methodology defined below, an identical nominal dose level is assumed. In the event that imbalance in the actual dose level is detected through observations documented in the summaries defined below, additional exploratory analyses should be conducted to adjust and account for this imbalance. For the multi-dose format of the study, the actual titer will be used in the model, rather than the nominal level.

Samples assessed for neurovirulence in this assay will be summarized as described below.

Descriptive Analyses

The number and percent of subjects providing a qualifying sample will be computed for each group. The study day from which the EES is produced will be summarized as a continuous variable and listed.

A neurovirulence endpoint assay result (NEAR) is defined as an assay result for a given EES and dose level of inoculum such that the accompanying high- and low-dose controls and the back-titration of inoculum are all within acceptable limits, per SOP. Each subject with a sample tested is anticipated to have 1 NEAR at the nominal single dose level of $4.0 \log_{10} \text{CCID}_{50}/\text{g}$. Additional NEARs at additional dose levels may also exist if the multidose format of the assay is initiated for a given subject/sample.

Assay results will be listed, including subject ID, vaccine group, study day of stool sample assayed, assay repeat number, the back-titration of inoculum, the nominal dose level of inoculum, the total number and percent of mice evaluable and paralyzed (also separately by mouse gender), the count and percent of accompanying high-and low-dose control mouse paralysis, a flag indicating if the assay lead to a re-test, a flag indicating if the assay lead to initiation of the multi-dose format of the assay, and a flag indicating whether the sample is a NEAR.

For NEARs, the number of mice evaluable for scoring as well as the number and percent of these mice paralyzed at each dose level tested (in the event multiple dose levels are used to inoculate groups of mice with a virus population obtained from a single subject) will be summarized (overall as well as by mouse gender), within vaccine group across subjects.

A boxplot of paralysis proportions will be prepared for each vaccine group wherever >2 subjects per dose level are available. Only NEARs using the $4.0 \log_{10} \text{CCID}_{50}/\text{g}$ dose level will contribute to this summary. Points will be overlaid on the boxplots.

Reasons for any sample re-runs, or initiation of the multi-dose format of the assay will be provided in a listing.

Model-based Analyses

If sufficient quantities of EES and, among them, sufficient mouse paralysis is observed, model-based analyses will be used to supplement the descriptive summaries described above. (See also the section *Alternate Method for Lack of Model Fit*, below.) It is currently known that, prior to the amplification step required to conduct the assay, only 2 post-dose-1 EES are available from the historical control subjects, UAM1. It is therefore likely that model-based analyses will fail, and/or will fail to provide additional insight beyond the descriptive summaries previously described, however, model-based analyses will still be attempted.

For each vaccine group, a generalized linear mixed model (GLMM) will be fitted to the binomial count of paralyzed mice for NEARs obtained at the $4.0 \log_{10} \text{CCID}_{50}/\text{g}$ dose level. This model is given by

$$\text{logit}^{-1}(p_i) = \beta_0 + \beta_1 I_{[\text{sex}=\text{F}]} + \delta_i \quad (1)$$

where

- β_0 is the overall mean log-odds of paralysis for male mice
- β_1 is the difference in mean log-odds of paralysis between mouse gender (females minus males)
- p_i is the paralysis rate for sample (subject) i
- $\delta_i \sim N(0, \tau^2)$ is the subject-level random effect, intended to capture overdispersion due to between-sample variability in the neurovirulence of each virus population, including variability in the precise titer of inoculum

In SAS/STAT software, this model may be fitted using the PROC GLIMMIX procedure. It is preferred to use METHOD = LAPLACE in the PROC GLIMMIX statement, due to better asymptotic performance of the estimators. The SAS default method for computing degrees of freedom should be utilized for statistical tests (DDFM = BETWITHIN). SAS code to fit the model defined above is given by:

```
proc glimmix data=dat method=laplace;
  class sample sex;
  model x/n = sex / cl solution ddfm = betwithin;
  random intercept / subject=sample;
  lsmeans sex / ilink;
run;
```

where “sample” is the sample number (e.g., subject identifier providing the sample), “x” is the mouse gender-specific number of mice paralyzed, “n” is the mouse gender-specific number of

inoculated mice available for analysis, and “sex” captures the mouse gender. The dataset “dat” should contain one row for each subject, for each mouse gender. Additional options to the SAS procedure may be necessary to obtain all necessary output.

Model fit results should be summarized in a table, including coefficient estimates and standard errors, p-values from *t*-tests of coefficients, and 95% confidence interval (based on the *t* distribution, the default for PROC GLIMMIX); similarly for the variance component. P-values for variance components will be based on the likelihood ratio test described by Molenberghs and Verbeke [2]. Additionally, the estimated mean paralysis rate per gender at the nominal dose level (4.0 log₁₀ CCID₅₀/g), will be obtained by inverting the logit transformation, and the delta method will be used to obtain its standard error, from which the 95% confidence interval will be obtained, utilizing asymptotic normality, and truncated at (0, 1) if necessary. A SAS LSMEANS statement will be used to obtain log-odds of paralysis averaged over mouse gender, and the corresponding probability and its 95% CI will be obtained via these same methods.

In the event that the multiple-dose format of the assay is employed for samples from one or more subjects, due to an excessive number of mice paralyzed (as defined in [1]):

1. The methods above will be employed, omitting the additional dose levels tested for those subject(s) *with* additional dose levels tested
2. The methods will be augmented with the analyses described in the *Statistical Methods for Multi-dose Assays* section below

Statistical Methods for Multi-dose Assays

In the event that the multiple dose format of the assay is employed for samples from one or more subjects, the GLMM described in (1) above will be augmented with a term for dose level as a continuous variable, and the NEARs will be modeled as:

$$\text{logit}^{-1}(p_{ij}) = \beta_0 + \beta_1 D_{ij} + \beta_2 I_{[sex=F]} + \delta_i \quad (2)$$

where

- β_0 is the overall mean log-odds of paralysis for male mice
- β_1 is the change in log-odds of paralysis associated with a unit increase in dose level of inoculum
- β_2 is the difference in mean log-odds of paralysis between mouse gender (females minus males)
- p_{ij} is the paralysis rate for sample *i* at dose level *j*
- D_{ij} indicates the *actual* (as opposed to nominal) dose level for sample *i*, indexed by *j*

- $\delta_i \sim N(0, \tau^2)$ is the subject-level random effect, intended to capture overdispersion due to between-sample variability in the neurovirulence of each virus population

In SAS/STAT software, this model may be fitted using the PROC GLIMMIX procedure. It is preferred to use METHOD = LAPLACE in the PROC GLIMMIX statement, due to better asymptotic performance of the estimators. The SAS default method for computing degrees of freedom should be utilized for statistical tests (DDFM = BETWITHIN). SAS code to fit the model defined above is given by:

```
proc glimmix data=dat method=laplace;
  class sample sex;
  model x/n = dose sex / cl solution ddfm = betwithin;
  random intercept / subject=sample;
run;
```

If only one subject for either vaccine group is available, then the random intercept term will be omitted. If subject numbers are low (e.g., ≤ 3), the GLMM may fail to fit due to numerical instability regarding the variance component. In this case also, the random intercept term will be omitted. Additional options to the SAS procedure may be necessary to obtain all necessary output.

Model fit results will be summarized in a table, including coefficient estimates and standard errors, p-values from t -tests of coefficients, and 95% confidence intervals for coefficients (based on the t distribution, the default for PROC GLIMMIX) as well as the variance component. P-values for variance components will be based on the likelihood ratio test described by Molenberghs and Verbeke [2]. Additionally, the fitted curve(s) will be plotted and accompanied by a descriptive legend, with important features such as the PD_{50} denoted in text on the plot. One curve for each subject will be shown (using estimates of the random effect terms), along with the mean curve in the case of more than 1 subject.

If any dose level produces $\geq 50\%$ of mice paralyzed, the estimated dose level corresponding to a 50% paralysis rate (PD_{50}) will be computed using inverse-prediction from the estimated model, omitting any variance components. The delta method and an assumption of asymptotic normality will be used to compute and present the standard error of this value and an accompanying 95% confidence interval, using Normal distribution critical values.

Alternate Method for Lack of Model Fit

It is expected that candidate vaccines will produce virus populations with low neurovirulence, and therefore it is possible that very few mice are paralyzed at the fixed dose level of inoculum (4.0 \log_{10} CCID₅₀), or at lower dose levels for either or both vaccine candidates. It is also possible that few subjects shed virus in sufficient quantity to enable the assay to be conducted. In either case, it is possible that the GLMM described above may not be able to be fitted to the data. In the event that paralysis proportions are low, the variance component will be difficult to fit. If the model is unable to be fitted using SAS default values for optimization convergence criteria, the following methods will be employed, in sequence, as backup:

1. The GLMM model will be reduced to a GLM model, by omitting the variance component term, and all methods above will be used. This method ignores the overdispersion expected by combining data from heterogeneous virus populations obtained from different subjects but will produce reliable estimates of mean paralysis rates if the contributions from each subject (sample size of mice) are relatively balanced, which is expected here. In this case, statistical inference would be affected, but the analysis is intended to be descriptive, rather than inferential.
2. In the event that 1) above fails to fit (due, for example, to *no* observation of paralysis), then all analysis will be limited to the descriptive analyses presented above equation (1)

Comparative Analysis for OPV-vaccinated subjects

In order to compare the neurovirulence of shed virus between each candidate vs the control, the following model will be fitted:

$$\text{logit}^{-1}(p_{hi}) = \beta_0 + \beta_1 I_{[h=2]} + \beta_2 I_{[sex=F]} + \delta_i \quad (3)$$

where

- h indexes virus ($h = 1$ = control vaccine [M1], $h = 2$ = candidate vaccine [M4])
- i indexes sample (subject) within levels of h
- β_0 is the overall mean log-odds of paralysis for shed virus samples for male mice, control vaccine
- β_1 is the difference in mean log-odds of paralysis between the two vaccines
- β_2 is the difference in mean log-odds of paralysis between mouse gender (females minus males)
- p_{hi} is the paralysis rate for virus source h , sample i
- $\delta_i \sim N(0, \tau^2)$ is the subject-level random effect for shed virus, intended to capture overdispersion due to between-sample variability in the neurovirulence of each virus population, including variability in the precise titer of inoculum, and is assumed common among all vaccine groups (but estimated uniquely in models for candidate 1 vs control, and candidate 2 vs control)

In SAS/STAT software, this model may be fitted using the PROC GLIMMIX procedure. It is preferred to use METHOD = LAPLACE in the PROC GLIMMIX statement, due to better asymptotic performance of the estimators. The SAS default method for computing degrees of freedom should be utilized for statistical tests (DDFM = BETWITHIN). SAS code to fit the model defined above is given by:

```
proc glimmix data=dat method=laplace;
  class sample vsource sex;
  model x/n = vsource sex / s cl solution ddfm = betwithin;
  random intercept / subject=sample;
  lsmeans vsource sex / cl ilink oddsratio e;
run;
```

where “sample” is the sample number (e.g., subject identifier providing the sample), “x” is the number of mice paralyzed, and “n” is the number of inoculated mice available for analysis, “vsouce” is a binary categorical (class) variable denoting whether the virus source is candidate vaccine or control, and “sex” is a categorical variable indicating the sex of the mice. The dataset “dat” should contain one row for each subject (or clinical supply sample) for each mouse gender. Additional options to the SAS procedure may be necessary to obtain all necessary output.

Model fit results should be summarized in a table, including coefficient estimates, standard errors, p-values for *t*-tests of coefficients, and 95% confidence interval (based on the *t* distribution, the default for PROC GLIMMIX) will be displayed for coefficients as well as for the variance components. For each candidate vaccine, the odds ratio (paralysis in each candidate vaccine group relative to the control group from study M1) and its corresponding two-sided 95% CI and two-sided p-value will be presented. P-values for variance components will be based on the likelihood ratio test described by Molenberghs and Verbeke [2]. Additionally, the estimated mean paralysis rate for each virus source h , \widehat{p}_h , will be obtained from the results of the SAS LSMEANS statement, and the delta method will be used to obtain the standard error, from which the 95% confidence intervals will be obtained, utilizing asymptotic normality, and truncated at (0, 1) if necessary. The odds ratio of paralysis between mouse genders, assumed common among vaccines groups, will also be presented as described for the gender-averaged probability.

As with other model-based methods above, if the model cannot be fit, remedies involve stepwise model simplification. For this model, the first simplification will be to reduce from a GLMM to a GLM via removal of the variance component. If that model cannot be fit, results will be limited to presentation of summaries described above equation (1) and augmented with the two-sided Fisher exact p-value arising from the cross-tabulation of paralyzed mice within each group, regardless of mouse gender and subject identifier, and the p-value will be regarded as approximate. If substantial imbalance in mouse availability rate is observed, additional sensitivity analyses may be added.

